14.2 Institutional Review Board

Informed consent, or IRB approved waiver of consent or altered consent process, is required for all subjects participating in a DMID-sponsored clinical trial, in compliance with applicable regulations and guidelines, including but not limited to 45 CFR 46, 21 CFR 50, 56, 312/812 for FDA-regulated studies, and ICH E6 Guidelines. Prior to the beginning of the trial, the investigator should have the IRB's written approval, favorable opinion of the written informed consent form(s), and any other written information to be provided to the subjects. The informed consent documents should meet the requirements of 21 CFR 50.20 and contain the information required of 21 CFR 50.25(a) and 21 CFR 50.25 (b). The relevant IRB will have the final authority for ensuring the adequacy of the information in the informed consent document.

Prior to enrollment of subjects into this study, the approved protocol and informed consent form will be reviewed and approved by the appropriate IRB listed on its FWA. The responsible official for the IRB will sign the IRB letter of approval of the protocol prior to the start of this study and a copy will be provided to DMID. The IRB FWA number will be provided to DMID.

Should amendments to the protocol be required, the amendments will be written by the sponsor and provided to the site principal investigator for submission to the IRB. A single IRB will be used for this study.

14.3 Informed Consent Process

The site principal investigators will choose subjects in accordance with the eligibility criteria detailed in [Section 5.1](#). Before any study procedures are performed, subjects must sign an informed consent form that complies with the requirements of 21 CFR Part 50 and 45 CFR 46 and the local IRB. Study personnel may employ recruitment efforts prior to obtaining study consent if a patient-specific screening consent is on record or if the IRB has agreed that chart review is allowed without a fully executed screening consent. In cases where there is not a patient-specific screening consent on record, site clinical staff may pre-screen via chart review and refer potential subjects to the research staff. Research staff would obtain written consent per the standard informed consent process before conducting protocol-specific screening activities.

Informed consent is a process that is initiated prior to an individual agreeing to participate in a study and continuing throughout the individual's study participation. Before any study procedures are performed, including pre-screening of subjects for eligibility, subjects will receive a comprehensive explanation of the proposed study procedures and study interventions/products. This will include the nature, risks and possible benefits of this study, alternate therapies, any known AEs, the investigational status of the study interventions/products, and the other elements that are part of obtaining proper informed consent. Subjects will also receive a detailed explanation of the proposed use and disclosure of their protected health information, including specifically their serum and urine samples. Subjects will be allowed sufficient time to consider participation in this research study, after having the nature, risks and possible benefits of this study explained to them, and can discuss this study with their family, friends or legally authorized representative or think about it prior to agreeing to participate.

Informed consent forms describing in detail the study interventions/products, study procedures, risks and possible benefits will be given to subjects. The informed consent form must not include any exculpatory statements. Informed consent forms will be IRB-approved and subjects will be asked to read and review the appropriate document. Upon reviewing the appropriate document, the site principal investigator (or designee) will explain this research study to subjects and answer any questions that may arise. Subjects must sign the informed consent form, and written documentation of the informed consent process is required prior to starting any study procedures specifically for this study, including determining eligibility and administering study product.

By signing the informed consent form, subjects agree to complete all study procedures required by this study, unless the subject withdraws voluntarily, or is withdrawn or terminated from this study for any reason. The rights and welfare of subjects will be protected by emphasizing to subjects that the quality of their medical care will not be adversely affected if they decline to participate in or withdraw from this study.

DMID will provide the site principal investigators, in writing, any new information that significantly impacts the subjects' risk of receiving the investigational products. This new information will be communicated by the site principal investigators to subjects who consent to participate in this study in accordance with IRB requirements. The informed consent document will be updated and subjects will be re-consented per IRB requirements, if necessary. Subjects will be given a copy of all informed consent forms that they sign.

14.4 Exclusion of Women, Minorities, and Children (Special Populations)

This study will be inclusive of all adults who meet the Subject Inclusion Criteria (see [Section 5.1](#)) and do not meet the Subject Exclusion Criteria (see [Section 5.2](#)), regardless of religion, sex, or ethnic background.

Women of childbearing potential who are not sterilized via tubal ligation, bilateral oophorectomy, salpingectomy, hysterectomy, or successful Essure[®] placement (permanent, non-surgical, non-hormonal sterilization) with documented radiological confirmation test at least 90 days after the procedure, and still menstruating or <1 year has passed since the last menses if menopausal must agree to practice highly effective contraception that may include, non-male sexual relationships, abstinence from sexual intercourse with a male partner, monogamous relationship with a vasectomized partner who has been vasectomized for 180 days or more prior to the subject receiving the study vaccination, barrier methods such as condoms or diaphragms/cervical cap **with** spermicide, effective intrauterine devices, NuvaRing[®], and licensed hormonal methods such as implants, injectables or oral contraceptives (the “pill”), with use of a highly effective method of contraception for a minimum of 30 days prior to study product exposure and agree to practice highly effective contraception for the duration of study product exposure, including 60 days after vaccination. A highly effective method of contraception is defined as one that results in a low failure rate (i.e., less than 1% per year) when used consistently and correctly. In addition to contraceptive use, all women of childbearing potential will be required to have a negative urine or serum pregnancy test within 24 hours prior to study vaccination. If a female subject becomes pregnant while participating in this study, we will ask her permission to follow-up with her about her health and the health of her baby through pregnancy outcome.

Children will not be included in this study.

14.5 Subject Confidentiality

Subject confidentiality is strictly held in trust by the site principal investigators, other study personnel, the sponsor, and their agents. This confidentiality is extended to cover testing of biological samples, in addition to the clinical information relating to participating subjects. Subjects will have code numbers and will not be identified by name.

The study protocol, documentation, data, and all other information generated will be held in strict confidence. No information concerning this study or the data will be released to any unauthorized third party without prior written approval of the sponsor.

All information provided by the sponsor and all data and information generated by the participating VTEU site as part of this study (other than a subject's medical records) will be kept confidential by the site principal investigators and other study personnel to the extent permitted by law. This information and data will not be used by the site principal investigator or other study personnel for any purpose other than conducting this study. These restrictions do not apply to: (1) information which becomes publicly available through no fault of the site principal investigator or other study personnel; (2) information which is necessary to disclose in confidence to an IRB solely for the evaluation of this study; (3) information which is necessary to disclose to provide appropriate medical care to a study subject; or (4) study results which may be published as described in [Section 16](#). The study monitor, applicable regulatory authorities, such as the FDA, or other authorized representatives of the sponsor may inspect all documents and records required to be maintained by the site principal investigators. This includes, but is not limited to, medical records (office, clinic, or hospital) and pharmacy records for the subjects in this study. The participating VTEU site will permit access to such records.

To protect privacy, we have received a Certificate of Confidentiality. With this Certificate, the researchers cannot be forced to release information that may identify the research subject, even by a court subpoena, in any federal, state, or local civil, criminal, administrative, legislative, or other proceedings. The researchers will use the Certificate to resist any demands for information that would identify the subject, except as explained below.

The Certificate cannot be used to resist a demand for information from personnel of the United States Government that is used for auditing or evaluation of federally funded projects, like this study, or for information that must be released in order to meet the requirements of the Federal Food and Drug Administration (FDA).

A Certificate of Confidentiality does not prevent the subject from voluntarily releasing information about themselves or their involvement in this research. If any person or agency obtains a written consent to receive research information, then the researchers may not use the Certificate to withhold that information.

The Certificate of Confidentiality does not prevent the researchers from reporting without the subject's consent, information that would identify the subject as a participant in the research project regarding matters that must be legally reported, including child and elder abuse, sexual abuse, or wanting to harm themselves or others.

14.6 Study Discontinuation

If the study is prematurely terminated by the sponsor, any regulatory authority, or the investigator for any reason, the investigator will promptly inform the study subjects and assure appropriate therapy or follow-up for the subjects, as necessary. The investigator will provide a detailed written explanation of the termination to the IRB. If any subject's private information will continue to be collected for this study, the IRB must approve a consent form with the study procedures, any risks and discomforts, and applicable elements, and the investigator or designee will re-consent the subjects as approved by the IRB.

14.7 Costs, Subject Compensation, and Research Related Injuries

There is no cost to subjects for the research tests, procedures, and study product while taking part in this trial. Procedures and treatment for clinical care may be billed to the subject, subject's insurance or third party. Subjects may be compensated for their participation in this trial. Compensation will be in accordance with the local IRB's policies and procedures, and subject to IRB approval.

If it is determined by the site principal investigator that an injury occurred to a subject as a direct result of the tests or treatments that are done for this trial, then referrals to appropriate health care facilities will be provided to the subject. Study personnel will try to reduce, control, and treat any complications from this trial. Immediate medical treatment may be provided by the participating site. No financial compensation will be provided to the subject by the NIAID, NIH to the subject, or by the participating site, for any injury suffered due to participation in this trial.

14.8 Future Use of Stored Specimens

Subjects will be asked for permission to keep any remaining serum from venous blood samples for possible use in future research studies, such as examining additional immunological assessments or testing for antibodies against other viruses or bacteria.

Additionally, subjects will be asked for permission to collect approximately 24 mL of additional venous blood for PBMC isolation and possible future research during Visits 1, 2, 4, 5 or, if applicable, during an early termination visit.

Samples will be stored indefinitely at a central clinical storage facility and may be shared with investigators at the participating VTEU site and with other investigators at other institutions. The samples will not be sold or used directly for production of any commercial product. No human genetic tests will be performed on the samples. Each sample will be encoded (labeled) only with a barcode and a unique tracking number to protect subject confidentiality.

There are no benefits to subjects in the collection, storage and subsequent use of their specimens for future research. Reports about future research done with subjects' samples will not be kept in their health records.

Subjects will be given the option to decide if they want their samples to be used for future research or have their samples destroyed at the end of this study. The subject's decision can be changed at any time by notifying the study doctors or nurses in writing; however, if a subject originally consents to future use and subsequently changes his/her decision, any data from a previously collected sample may still be used for this research.

15 DATA HANDLING AND RECORD KEEPING

The site principal investigator is responsible to ensure the accuracy, completeness, legibility, and timeliness of the data reported.

Data collection forms will be derived from the eCRF and provided by the DCC to record and maintain data for each subject enrolled in this study. All data collection forms should be completed in a neat, legible manner to ensure accurate interpretation of data. Black or blue ink is required to ensure clarity of reproduced copies. When making a change or correction, cross out the original entry with a single line and initial and date the change. Do not erase, overwrite, or use correction fluid or tape on the original.

Data reported in the eCRF derived from the data collection forms should be consistent with the data collection forms or the discrepancies should be explained.

The sponsor and/or its designee will provide guidance to the site principal investigators and other study personnel on making corrections to the data collection forms and eCRF.

15.1 Data Management Responsibilities

All data collection forms and laboratory reports must be reviewed by the clinical team and data entry personnel, who will ensure that they are accurate and complete. Adverse events must be recorded on the appropriate data collection form, assessed for severity and relationship, and reviewed by the site principal investigator or appropriate sub-investigator.

Data collection is the responsibility of the study personnel at the participating VTEU site under the supervision of the respective site principal investigators. During this study, the site principal investigators must maintain complete and accurate documentation for this study.

The DCC for this study will be responsible for data management, quality review, analysis, and reporting of the study data.

15.2 Data Capture Methods

Clinical (including, but not limited to, AE/SAEs, concomitant medications, medical history, and physical assessments), reactogenicity, serologic immunogenicity, and mucosal immunogenicity data will be entered into a 21 CFR 11-compliant Internet Data Entry System provided by the DCC. The data system includes password protection and internal quality checks, such as automatic range checks, to identify data that appear inconsistent, incomplete, or inaccurate.

Clinical and reactogenicity data will be entered directly from the data collection forms completed by the study personnel.

15.3 Types of Data

Data for this study will include clinical, safety, and outcome measures (e.g., reactogenicity, serologic immunogenicity/mucosal immunogenicity [antibody assays], and shedding of BPZE1 from nasal samples).

15.4 Timing/Reports

A preliminary analysis will be performed when all safety, reactogenicity, immunogenicity and *B. pertussis* colonization data through Day 46 (or Day 29 if no subjects remain colonized with *B. pertussis* at Day 29) are available. Analyses will be made available to DMID, the lead principal investigator, and vaccine company partner for planning subsequent clinical trials. These analyses will not be used to make any decisions concerning the conduct of this trial. As it is anticipated that subjects will remain in long term follow-up at the time of these analyses, blinded investigators who will not be involved in the analysis will be responsible for assessing SAEs and AESIs until all subjects have completed the final follow-up visit.

Other interim statistical reports may be generated as deemed necessary and appropriate by DMID. Safety and immunogenicity summary reports may be generated for the SMC, as well. See [Section 9.3](#) for further reporting details.

The final clinical study report (CSR) will be completed when all clinical, safety, and reactogenicity data through approximately 180 days after the study vaccination are available. Once the last subject completes the last visit, the final clinical database will be cleaned, monitored and locked. Unblinded analyses of safety, reactogenicity, colonization, and available immunogenicity data will then be performed by the DCC and will be included in the CSR.

After full analysis and final reporting is complete, and upon request and DMID approval, the DCC will provide the participating VTEU site with a summary of results by treatment arm and/or subject treatment assignments. In this regard, the participating VTEU site requesting such information to share with study subjects must do so in compliance with their respective IRB guidelines.

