3.2 Study Outcome Measures

3.2.1 Primary Outcome Measures

1. Occurrence of solicited local and systemic reactogenicity from the time of the study vaccination through 14 days post-vaccination
2. Occurrence of unsolicited non-serious adverse events from the time of the study vaccination through 28 days post-vaccination
3. Occurrence of serious adverse events (SAEs) and new onset chronic medical conditions (NOCMCs) from the time of the study vaccination through approximately Day 181 post vaccination
4. Occurrence of adverse events of special interest through approximately Day 29 post vaccination

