7.3.3 Visit 4, Day 29, Clinic Visit (Window: Day 29 ± 3 days)

- Interim medical history, including an assessment for new medical conditions, will be obtained by interview of subjects and any changes since the previous clinic visit or contact will be noted.
- All concomitant medications and vaccines will be recorded on the appropriate data collection form.
- All AE/SAEs will be recorded on the appropriate data collection form.
- A targeted physical examination may be performed, if indicated based on review of interim medical history, by a study clinician.
- Approximately 10 mL of venous blood will be collected for antibody assays.

-
- For subjects who consent to additional future use samples, approximately 24 mL of venous blood will be collected for PMBC isolation and possible future research.
 - Nasal samples will be obtained for *B. pertussis* culture and immunological assays. If culture is positive for *B. pertussis*, the isolate will be cryopreserved as detailed in the MOP.

7.3.4 Visit 4a (If needed, based on *B. pertussis* positive culture on Day 29), Day 46, Clinic Visit (Day 46 ± 3 days)

- Interim medical history, including an assessment for new medical conditions, will be obtained by interview of subjects and any changes since the previous clinic visit or contact will be noted.
- All concomitant vaccines will be recorded on the appropriate data collection form.
- All SAEs will be recorded on the appropriate data collection form.
- A targeted physical examination may be performed, if indicated based on review of interim medical history, by a study clinician.
- Nasal samples will be obtained for *B. pertussis* culture (if necessary-positive from day 29) and immunological assays. If culture is positive for *B. pertussis*, the isolate will be cryopreserved as detailed in the MOP.

7.3.5 Visit 4b (if needed, based on positive *B. pertussis* culture from Day 46), Day 50, Phone Call (Day 50 ± 3 days)

- If a participant's sample from Visit 4a is positive for *B. pertussis*, a study investigator will prescribe a 5-day course of azithromycin (500 mg orally once per day).

7.4 Final Study Visit, Visit 5, Day 181, Clinic Visit (Day 181 ± 21 days)

- Interim medical history, including an assessment for new medical conditions, will be obtained by interview of subjects and any changes since the previous clinic visit or contact will be noted.
- All concomitant vaccines will be recorded on the appropriate data collection form.

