9.2.4 New Onset Chronic Medical Conditions

The development of new onset chronic medical conditions will be assessed through Day 181. These are defined as new medical conditions, not present at the time of screening or enrollment, that require ongoing medical care and intervention.

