9.2.5 Adverse Events of Special Interest

Medically attended wheezing events will be considered adverse events of special interest given the route of study product administration and the nature of the study product (i.e., a live attenuated bacterial vaccine). Though subjects with a history of persistent asthma will be excluded from the study, it is possible that new onset wheezing episodes could occur. These will be evaluated by a study investigator and relatedness to study product will be assessed. Medically attended wheezing events will be evaluated through Day 29.

9.2.6 Procedures to be Followed in the Event of Abnormal Laboratory Test Values or Abnormal Clinical Findings

Solicited mucosal site and systemic reactogenicity events will be documented and reported from the time of study vaccination through 14 days (Day 15) after study vaccination.

Unsolicited, non-serious AEs will be documented from the time of study vaccination through approximately 28 days (Day 29) after study vaccination.

SAEs will be documented from the time of study vaccination through approximately 6 months post vaccination.

[figure not shown]
In addition, if a subject has an abnormal laboratory test value (e.g., complete blood count or serum chemistries), it will be recorded as an AE and will be graded per toxicity table and will be followed up until resolution.

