11.4 Final Analysis Plan

The results obtained from this study will be used to inform the dose recommended for a subsequent Phase 2b study. Clinical, safety, reactogenicity, immunogenicity and *B. pertussis* colonization data through approximately 45 days after study vaccination, or 28 days after study vaccination if no subjects remain colonized with *B. pertussis* at Day 29, will represent the primary clinical database for this trial. Once the last subject completes the visit that occurs approximately 45 days after study vaccination (or approximately 28 days after study vaccination, if no subjects remain colonized with *B. pertussis* at the Day 29 visit), the primary clinical database will be cleaned, monitored, and frozen. Analyses of safety, reactogenicity, immunogenicity, and *B. pertussis* colonization data by treatment arm are planned, including descriptive summaries of 15-day reactogenicity data, 28-day adverse event data (including SAE, NOCMC and AESI), 28 and 45-day nasal clearance data, and humoral and mucosal immunogenicity data through Day 46 (or Day 29 if no subjects remain colonized with *B. pertussis* at the Day 29 visit). As it is anticipated that subjects will remain in long term immunogenicity and safety follow-up at the time of these analyses, the presentation of these data will not include any unblinded listings of individual subject data and aggregate summaries will be in a format that prevents inadvertent unblinding of the sponsor or clinical investigators to any individual subject's treatment assignment or immune response data.

A preliminary report will be prepared by the DCC after the primary clinical database is cleaned, monitored, and frozen and all immunogenicity and colonization data through Day 46 (or Day 29 if no subjects remain colonized with *B. pertussis* at the Day 29 visit) are received. These analyses may be made available to DMID and the vaccine company partner and to the lead principal investigator for planning subsequent trials. These analyses will not be used to make any decisions concerning the conduct of this trial. A formal statistical analysis plan that defines the analyses of data to be included in the preliminary report for early release and the CSR will be developed and finalized prior to the to the Day 46 data freeze (or Day 29 if no subjects remain colonized with *B. pertussis* at the Day 29 visit).

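### After the preliminary by-arm release, the blinded-assessor rule omits new onset chronic medical conditions, a primary outcome open to Day 181, and starred SAP listings would unblind subjects with events

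*Protocol*

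**What the plan says.** **Release of results.** Protocol Section 15.4 provides for a preliminary analysis once data through Day 46 are in, or through Day 29 if nobody is still colonised. It states: "Analyses will be made available to DMID, the lead principal investigator, and vaccine company partner for planning subsequent clinical trials". Section 11.4 confirms that analyses of safety, immunogenicity and "colonization data by treatment arm are planned". The trial has one site.

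**Safeguard 1, assessors (Section 15.4).** Because subjects will still be in follow-up, "blinded investigators who will not be involved in the analysis will be responsible for assessing SAEs and AESIs until all subjects have completed" their last visit.

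**Safeguard 2, format (Section 11.4).** The preliminary presentation is to contain no unblinded listings of individual subjects, and its summaries must not reveal any one subject's allocation.

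**Outcome windows.** Section 3.2.1 lists as primary outcomes "Occurrence of serious adverse events (SAEs) and new onset chronic medical conditions (NOCMCs) from the time of the study vaccination through approximately Day 181" and "Occurrence of adverse events of special interest through approximately Day 29 post vaccination". Section 9.2.4 agrees on the first: "The development of new onset chronic medical conditions will be assessed through Day 181". Section 9.2.5 agrees on the second: "Medically attended wheezing events will be evaluated through Day 29". The Appendix A footnote on AE/SAE assessment, repeated under SAP Table 1, instead puts AESIs with NOCMCs and SAEs among the events assessed after Day 28.

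**SAP tables.** SAP Appendix 1 says that starred tables go into the Preliminary Report. Tables 56 (SAEs), 57 (unsolicited non-serious AEs) and 58 (NOCMCs and AESIs) are starred. Each entry is headed by treatment group and subject ID.

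**Culture.** Section 3.2.2 attributes any detected *B. pertussis* to study product. A positive Day 29 culture triggers Visit 4a. Visit 4a has the same history item as the Day 29 visit: "Interim medical history, including an assessment for new medical conditions, will be obtained by interview of subjects".

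**The concern.** Once by-arm results have been released, the primary outcomes still being collected are SAEs and NOCMCs. The assessor rule covers the first and not the second. An NOCMC that is also serious is protected as an SAE; a non-serious one is not.

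This matters because an NOCMC involves judgement. Someone must decide whether a complaint is new and needs continuing care, and SAP Table 58 also records its relationship to study product. Under Section 9.2.1, severity and relationship are judged by the site principal investigator or a sub-investigator. Nothing in Section 15.4 stops a person who has read the preliminary report from making that judgement for an NOCMC.

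The format safeguard should limit the damage, but the SAP works against it. A report containing Tables 56 to 58 as drawn would link subject IDs to arms, and Table 58 does so for the outcome that the assessor rule leaves out.

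The culture result is a second and narrower route. Section 5.3.2 keeps investigators blind to BPZE1 versus placebo, but a positive culture discloses BPZE1 for that subject.

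**Working it through.** The plan gives no figure on this point to reproduce. The check compares time windows and then sizes the exposure.

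**1. Safeguard against windows**

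| Outcome | Window | Open after release? | Named in 15.4? |
|---|---|---|---|
| SAEs | to about Day 181 | Yes | Yes |
| NOCMCs | to about Day 181 | Yes | No |
| AESIs (3.2.1, 9.1, 9.2.5) | to about Day 29 | No | Yes |
| AESIs (Appendix A footnote) | also after Day 28 | Possibly | Yes |

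NOCMCs are open and unnamed whichever AESI window is right. After Day 29 the NOCMC window runs for 181 − 29 = 152 of the 180 days after vaccination (152/180 = 84%).

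**2. Preliminary Report contents**

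The SAP marks differences for the preliminary report when it intends them. Tables 17, 21, 25, 29 and 31 have a footnote that drops Day 181, and the subject-level laboratory listings (Tables 59 and 60) are not starred. Tables 56 to 58 are starred and have no note removing treatment group or subject ID. SAP Appendix 3 keeps its own listings out of the report, but these three tables are in Appendix 1.

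**3. Subjects still in follow-up**

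The trigger is the last subject reaching day *d* (29 or 46). With uniform accrual over *A* days (assumed) and a lag of *L* days before release:

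number remaining = 50 × (181 − *d* − *L*) / *A*

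The protocol gives two accrual periods: about 12 months (Section 4; *A* = 365) and about 6 months (Section 5; *A* = 182.5).

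| *A* | *d* | *L* = 0 | *L* = 90 (assumed) |
|---|---|---|---|
| 365 | 46 | 50 × 135/365 = 18.5 | 50 × 45/365 = 6.2 |
| 365 | 29 | 50 × 152/365 = 20.8 | 50 × 62/365 = 8.5 |
| 182.5 | 46 | 50 × 135/182.5 = 37.0 | 50 × 45/182.5 = 12.3 |
| 182.5 | 29 | 50 × 152/182.5 = 41.6 | 50 × 62/182.5 = 17.0 |

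The longest exposure for one subject is 152 days from a Day 29 trigger or 135 days from a Day 46 trigger, before any lag.

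**4. What a Day 29 culture reveals**

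The three VaxINator arms have 30 BPZE1 and 15 placebo subjects, so the prior probability of BPZE1 is 30/45 = 0.667. The five syringe subjects are already known to be on BPZE1 from the device. Let *p* be the Day 29 positive rate among BPZE1 recipients. The documents give no value, so 0 to 20% is assumed, with no positives on placebo.

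- After a positive, P(BPZE1) = 1.
- After a negative, P(BPZE1) = 30(1 − *p*) / [30(1 − *p*) + 15].
- Chance of at least one positive = 1 − (1 − *p*)^30.

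| *p* | Expected positives of 30 | Chance of at least one | P(BPZE1) after a negative |
|---|---|---|---|
| 0% | 0 | 0% | 0.667 |
| 5% | 1.5 | 79% | 0.655 |
| 10% | 3 | 96% | 0.643 |
| 20% | 6 | 99.9% | 0.615 |

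Over this range, 24 to 30 of the 30 blinded recipients are not revealed by an individual positive culture.

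**The case against.** The strongest reply is that Section 11.4 already protects individual allocation. Aggregate arm results do not show which arm a given subject is in, and that section and SAP Section 2.1 say only that the analyses may be shared. That would carry weight if the SAP carried it out. Starred Tables 56 to 58 do the opposite, and the protocol itself did not rely on format alone, since Section 15.4 adds blinded assessors. The omission of NOCMCs stands.

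It can also be said that the trial tests no formal hypothesis (Section 11.1) and that NOCMCs have a written definition. Both are true and both limit the harm. Neither removes the judgement about relationship.

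Three stronger readings are tempting, and the documents do not support them:

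- *The AESI half of the safeguard is empty.* That follows from Sections 3.2.1, 9.1 and 9.2.5 but conflicts with the Appendix A footnote. The passages must be reconciled before anyone can say so.
- *Day 29 cultures show the site who received BPZE1.* They identify positives only and do not separate the two doses. Section 2.3.1.2 says the vast majority of earlier subjects were clear by Day 29, and Section 2.1.2 has Phase 1b colonisation lasting to day 11 to 28. A negative tells the assessor little. Who at the site receives the Day 29 result, and whether that person later assesses events, is not stated.
- *All 50 subjects are exposed.* Neither stated accrual period gives that under uniform accrual.

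**Conclusion.** The point holds in this form. Section 15.4 leaves out a primary outcome that remains open after by-arm results reach the lead investigator at the only site. The SAP's preliminary tables, as specified, would unblind individual subjects with events, including NOCMCs, contrary to Section 11.4. These two findings rest on the text and need no assumption.

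The size is modest. With uniform accrual assumed, about 18 to 42 subjects are still in follow-up at the data trigger, and about 6 to 17 if cleaning and assay receipt take an assumed 90 days. One reclassified NOCMC moves an arm of 15 by 1/15 = 6.7 percentage points; that is the granularity of the outcome, not an estimate of bias. The culture route is real but secondary: 0 to 6 expected positives among the 30 blinded recipients at an assumed 0 to 20% positive rate. A reader might infer that safety assessments will be biased. The documents show an unprotected judgement, not a bias.

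**What to change.** 1. In Protocol Section 15.4, extend the blinded-assessor sentence to *SAEs, NOCMCs and any AESI still open*.
2. Reconcile the AESI window between Sections 3.2.1, 9.1 and 9.2.5 and the Appendix A footnote, and carry the result into the footnote under SAP Table 1.
3. In the SAP, remove treatment group and subject ID from Tables 56 to 58 for the Preliminary Report, or remove their asterisks and hold them for the CSR.
4. Where feasible, have severity and relatedness of Day 1 to 29 events recorded before the assessor sees the Day 29 culture result, without delaying any result needed for a subject's care.

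Routing culture results through the unblinded staff is not worth proposing. Visit 4a takes place only for Day 29 positives, so holding it already discloses the result to whoever conducts it. Section 5.3.2 also bars the unblinded vaccine administrator from later subject contact for data collection.

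The cost is a few sentences, minor table-shell edits and slightly less detail in the Preliminary Report. No visits, samples or subjects are added.
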